6.6.2 Pharmacokinetics

PK trough values at steady state for ofatumumab will be used to conduct a population pharmacokinetics analysis. Sampling time points are provided in [Table 6-1](#). Samples for PK assessment should be taken prior to dosing at the Month 1 visit. For any later PK visits, if the visit coincides with the day the monthly injection is scheduled, the patient should not take the injection in the morning before coming to the site so that the PK sample can be drawn before the injection. The PK sample collection date and time must be entered on the appropriate CRF.

Further details on sample collection, numbering, processing and shipment will be provided in the Laboratory Manual provided to the sites.

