6.6.3 Immunogenicity

ADA will be assessed to evaluate the immunogenicity potential of ofatumumab. Sampling time points are provided in [Table 6-1](#). Samples for ADA assessment should be taken prior to dosing at the Month 1 visit. For any later ADA visits, if the visit coincides with the day the monthly injection is scheduled, the patient should not take the injection in the morning before coming to the site so that the ADA sample can be drawn before the injection. The ADA sample collection date and time must be entered on the appropriate CRF.

7 Safety monitoring

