9.1 Analysis sets

Full analysis set (FAS): The FAS comprises all randomized subjects with assigned treatments. Subjects will be analyzed according to the randomized treatment assignment following the intention-to-treat (ITT) principle, even if they actually received a different treatment.

The FAS will be used for the summary of demography and baseline characteristics as well as for all efficacy analyses.

Per-protocol set (PPS): The PPS is a subset of FAS, consists of all randomized subjects who take at least one dose of study medication and have no major protocol deviations that could confound the interpretation of analyses conducted on the FAS. Major protocol deviations will be determined according to the pre-defined protocol deviation criteria before treatment unblinding (e.g. non-compliance for a large proportion of the time in study). For analyses performed on the PPS, only on-treatment assessments will be used.

The PPS will primarily be used for the supportive analyses of the primary efficacy variable and selected key secondary variables.

Safety set (SAF): The SAF set includes all subjects who received at least one dose of study medication. Subjects will be analyzed according to the actual treatment received. The Safety Set will be used for all safety analyses.

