Baseline	Baseline is the last assessment obtained prior to the first administration of study drug. No visit windows will be needed for the identification of baseline assessment. For pulse and blood pressure vital sign values, the baseline is the average of the non-missing values of the 3 measurements taken on the last visit prior to the first administration of study drug. The pre-injection assessment values on Day 1 vital sign CRF page will not be used for baseline derivations.
On-treatment period	For patients randomized to receive ofatumumab, on-treatment period includes days from the first injection date until 30 days after the last injection date; for patients randomized to receive teriflunomide, on-treatment period includes days from the first dose date until the last dose date. This definition considers patients on ofatumumab are scheduled to inject every 28 +/- 3 days. The on-treatment definition applies to efficacy analyses only. For calculation of compliance to study drug administration, similar definition of on-treatment period except based on actual treatment assignment will be used.
Safety cutoff (off-treatment)	Safety cutoff: Unless explicitly otherwise stated (e.g. SAEs and deaths), data up to and including the safety cutoff of 100 days after permanent study drug discontinuation will be

	included in the analysis and data beyond this time point for a given patient will be excluded from the safety analysis. The safety cutoff of 100 days (5x20 days) takes the long half-life of both investigational and comparator-drug into account. The safety cutoff applies to safety analyses only.
Nominal visits	Nominal visits are defined as all scheduled visits as per the clinical study protocol including the EOS and EOT visits. The definition of nominal visit excludes unscheduled visits. Only vital signs data collected on Day 1, Day 7, Day 14 and Month 1 protocol scheduled visit and ECG data collected on EOT and EOS visits will be summarized by nominal visit.
End of Study (EOS)	EOS, used in the context of individual patients, refers to EOS visit. EOS, used in the context of the entire study, refers to completion of treatment epoch for all patients.
End of Treatment (EOT)	EOT refers to EOT visit. Only patients who prematurely discontinue study drug but agree to continue to follow the schedule of assessments in the treatment epoch will have EOT visit.

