2.1.2 Visit windows

2.1.2.1 Visit windows for treatment epoch

Visit-windows will be used for both efficacy and safety data summaries by visit. Visit windows define a time period “around” the targeted visit date as defined in the evaluation schedule of the clinical study protocol. Visit-windows are non-overlapping, and defined without gaps between consecutive visit windows. The width of visit windows may vary over the course of the study period.

Baseline assessments are defined in [Section 2.1.1](#) and do not require a visit window.

The purpose of visit windows is to analyze data based on the actual study days (rather than "nominal" visits). E.g., if a patient’s Month 1 visit is delayed; it is possible that the Month 1 data be re-aligned to visit-window Month 2 and be summarized under Month 2.

- For **efficacy analyses** (including PK concentration by visit analysis) all nominal visits (i.e. excluding unscheduled visits) will be mapped into one of the defined visit-windows. Note: for the derivation of disability worsening or improvement all visits (scheduled and unscheduled) need to be considered before the worsening or improvement can be confirmed (see [Section 2.6.1.1](#)). Similarly, for No Evidence of Disease Activity (NEDA-4), all visits (scheduled and unscheduled) need to be considered ([Section 2.7.1](#)).

-For **safety analyses** all visits (scheduled and unscheduled) will be mapped to visit windows. Safety data from unscheduled visits may be reported separately if applicable.

It is possible that more than one assessment of a patient fall into a particular visit-window. [Section 2.1.2.3](#) deals with the statistical approaches to handle multiple visits in a given visit-window.

Tables displaying summary statistics “by visit” will also use the term *visit-window* as column header; this is to remind the reviewer that multiple assessments of a patient might be summarized. Below tables provide visit-windows definitions for applicable parameters.

Table 2-3 Visit-windows for EDSS*/T25FW

Visit-window	Start day	Target Day	End day
Week 12	1	84	126
Week 24	127	168	210
Week 36	211	252	294
Week 48	295	336	378
Week 60	379	420	462
Week 72	463	504	546
Week 84	547	588	630
Week 96	631	672	714
Week 108	715	756	798
Week 120	799	840	881

* For EDSS, assessment on Day 1 will be excluded as baseline EDSS can occur on Day 1 per protocol.

Table 2-4 Visit-windows for 9HPT/SDMT/MSIS-29/

Visit-window	Start day	Target Day	End day
Week 24	1	168	252

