2.8.3.4 Other special lab results

Other non-routine laboratory data include pregnancy test results, B-cell counts, teriflunomide plasma levels, total IgG, total IgM, [REDACTED]. All data will be listed appropriately.

The B-cell counts, total IgG, total IgM, neurofilaments [REDACTED] will be summarized using descriptive statistics by treatment group and visit-window.

In addition, number and percentage of patients with B-cells < the lower limit of normal (LLN) value (i.e., B-cell depleted) will be presented by treatment group and visit-window. Graphic presentation of B-cell counts distribution will also be provided by treatment group and visit-window. All B-cell summaries defined in this section will include data up to the end of the on-treatment period (i.e., last dose date + 30). This is to provide more accurate information about B-cell depletion because fast B-cell repletion is expected after study drug discontinuation and applying the safety cutoff (i.e., last dose date +100) would mix repletion and depletion to some degree.

Number and percentage of patients meeting the notable low level criteria in IgG or IgM at least once will be provided by treatment group. A notably low IgG level is defined as a level that is 20% below the LLN and a notably low IgM level is defined as a level 10% below the LLN.

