2.9 Pharmacokinetic endpoints

2.9.2 Immunogenicity assessment

Samples will be analyzed for the presence of human anti-drug antibodies (ADA). The data will be summarized by visit and overall (i.e. proportion of patients with ADA) as an assessment of the immunogenicity potential of ofatumumab. A listing by patient will also be provided. All patients in FAS with non-missing values will be included in these analyses.

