2.10 PD and PK/PD analyses and modelling

PK concentration data summarized by visit together with by-patient listings will be provided in the study report. All patients in FAS with non-missing values will be included in these analyses.

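### By-visit ofatumumab concentrations carry no visible on-treatment limit, and the overall ADA proportion does not separate baseline antibodies from those arising on treatment

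*Protocol*

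**What the plan says.** **PK.** Evaluating ofatumumab PK is a secondary objective (Protocol 2.2). Protocol 6.6.2 describes the input to the population model: "PK trough values at steady state for ofatumumab will be used to conduct a population pharmacokinetics analysis". Sample date and time go on the CRF. Pre-dose sampling is required at Month 1; at later visits it is asked for only when the injection is due that day. Table 6-1 places PK samples at baseline, Months 1, 3, 6, 12 and 24, EOT and EOS.

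SAP 2.10 adds a table of concentrations by visit, with listings. Its population is stated as: "All patients in FAS with non-missing values will be included in these analyses". SAP 2.1.2.1 places this table among the efficacy analyses ("including PK concentration by visit analysis) all nominal visits (i.e. excluding unscheduled visits) will be mapped into one of the defined visit-windows"), and SAP 2.1.1 adds: "Nominal visits are defined as all scheduled visits as per the clinical study protocol including the EOS and EOT visits". For efficacy analyses on the FAS, SAP 2.1 uses data to the end of the treatment epoch with no other cut-off. The FAS follows the randomised arm: "Subjects will be analyzed according to the randomized treatment assignment following the intention-to-treat (ITT) principle, even if they actually received a different treatment" (Protocol 9.1).

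**B-cells, for contrast.** SAP 2.8.3.4 stops the B-cell summaries at last dose + 30 days, because "applying the safety cutoff (i.e., last dose date +100) would mix repletion and depletion to some degree".

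**ADA.** The purpose in Protocol 6.6.3 is: "ADA will be assessed to evaluate the immunogenicity potential of ofatumumab". Samples are taken at baseline, Months 1, 6, 12 and 24, EOT and EOS. SAP 2.9.2 says: "The data will be summarized by visit and overall (i.e. proportion of patients with ADA) as an assessment of the immunogenicity potential". It uses the same FAS population and promises a by-patient listing. The visible text has no category for baseline-positive or treatment-emergent ADA.

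**The concern.** A by-visit concentration row is normally read as exposure under continued dosing. If some values come from patients who have stopped ofatumumab, the row is pulled down by washout. If others are drawn mid-interval, it is pulled up relative to trough. The two effects can offset each other, so the printed mean or median would not reveal either.

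The overall ADA proportion is offered as the measure of ofatumumab's immunogenicity. Antibodies already present before the first dose say nothing about that. Protocol 1.1 expects a very low incidence (under 1% in oncology studies), so a handful of pre-existing positives could make up much of the figure.

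At stake is the reading of one secondary objective and one standard immunogenicity statistic. No hypothesis test depends on either.

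**Working it through.** The plan attaches no sample size, power or error rate to these summaries, so there is no figure of its own to reproduce. The check is day arithmetic plus two illustrations on stated assumptions.

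**1. Which samples can enter a PK row.** Analysis windows from SAP Table 2-11:

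| Row | Days | Length (days) | Length / 28 |
|---|---|---|---|
| Week 4 | 1–56 | 56 | 2.0 |
| Week 12 | 57–126 | 70 | 2.5 |
| Week 24 | 127–252 | 126 | 4.5 |
| Week 48 | 253–504 | 252 | 9.0 |
| Week 96 | 505–839 | 335 | 12.0 |

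Table 6-1 gives EOT and EOS no visit window, so those samples fall in whichever row contains their day. SAP 2.1.2.3 then takes one value per row, the one closest to target.

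**2. Whether closest-to-target selection protects the row.** Take a constructed patient with a last injection on day 532 (19 × 28), an EOT sample on day 560 and an EOS sample on day 644. Both samples fall in Week 96 (target 672).
- EOT: |560 − 672| = 112 days from target; 560 − 532 = 28 days after the last injection.
- EOS: |644 − 672| = 28 days from target; 644 − 532 = 112 days after the last injection.

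The rule picks the EOS value, which is off drug, over the EOT value, which is a trough. A limit at day 532 + 30 = 562 would reverse this. The example assumes that a patient who stopped drug still gives a PK sample at EOS.

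**3. Size of an off-drug value (illustration).** Relative to the day-28 trough, concentration at t days since injection is 2^((28 − t)/h), where h is the half-life and absorption is ignored. The documents give no ofatumumab half-life as such. SAP 2.1.1 ties its 5 × 20-day cut-off to both drugs, so I use h = 20 with a range of 30 to 10. At t = 112: 2^(−84/20) = 0.054, about 5% of trough (14% to 0.3% over the range).

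**4. Position within the dosing interval.** The PK target days 28, 84, 168, 336 and 672 are all multiples of 28, so an on-target visit coincides with a due injection. The Month 1 window (±3 days) spans 6/28 = 21% of the interval. From Month 3, ±14 days spans 28/28 = 100%. With the same formula and h = 20:
- t = 14: 2^(14/20) = 1.62 times trough (1.38 to 2.64 for h = 30 to 10)
- t = 7: 2^(21/20) = 2.07 times trough (1.62 to 4.29)

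How many samples lie near trough depends on attendance, which is not documented. Assume injections on the due date and a sample taken pre-dose if the visit is at most 3 days late.
- Attendance uniform over the 29 whole-day offsets: 7/29 = 24% fall 25–31 days after the last injection and 11/29 = 38% are post-dose.
- Attendance normal with SD 4 days, rounded to whole days: 2Φ(3.5/4) − 1 = 62% and 1 − Φ(3.5/4) = 19%.

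**5. ADA (illustration, rates assumed).** Let b be the proportion positive at baseline and i the proportion induced among the rest. If baseline positives count, the overall proportion is b + (1 − b)i.
- b = 1%, i = 1%: 0.01 + 0.99 × 0.01 = 1.99%, of which 0.01/0.0199 = 50% is pre-existing.
- b = 5%, i = 0.2%: 0.05 + 0.95 × 0.002 = 5.19%, of which 96% is pre-existing.
- b = 0: nothing is pre-existing and the issue vanishes.

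For scale, under 1% of 450 patients is fewer than 5.

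**The case against.** The strongest reply is that little may go wrong in practice, and that some of the relevant text cannot be seen.

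- **No table claims to show steady-state trough.** A reader might infer this from Protocol 6.6.2, but that sentence concerns the population PK model, which can use the recorded times. This stands.
- **Not every measured value is used.** Unscheduled visits are excluded and one value is taken per window. This stands, but step 2 shows that it does not keep off-drug values out.
- **Post-discontinuation sampling is uncertain.** Patients followed after EOT do only the shaded assessments in Table 6-1, and the shading is not legible here. EOT visits are meant to be prompt. This limits any claim about frequency. The EOT sample can still follow the last dose, as can the EOS sample of a patient who stops drug and leaves the treatment epoch.
- **Dropout does not give the off-drug share.** A reader might carry over the 20% dropout assumption. Patients who leave the study give no later samples, so that inference fails.
- **Adjacent text is missing.** The SAP passage before 2.9.2 and part of Protocol 9.5.5 are not shown. If a timing rule stands there, citing it answers the PK part.
- **Baseline ADA can be recovered from the listing**, and the text does not say that the overall figure counts patients positive only at baseline. Both are true. But a patient positive at baseline who stays positive would count even if only post-baseline samples were used, and a listing does not pre-specify the headline figure.

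**Conclusion.** The point holds as a gap in the visible plan. Followed as written, SAP 2.10 allows off-drug values into the Week 12 to Week 96 rows and leaves the rows from Month 3 onward a mixture of times within the dosing interval. SAP 2.9.2 gives an overall ADA proportion that does not isolate antibodies arising on treatment. The sponsor's own reasoning for the B-cell summaries applies equally to concentrations.

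The size is not known. The illustrated ratios (about 5% of trough off drug, 1.62 times at mid-interval) rest on an assumed half-life and simple exponential decline. The ADA shares rest on assumed rates. A reader might go further and infer that the by-visit means are wrong by a known multiple, or that baseline positives will outnumber induced cases. The documents support neither. They also give no rate of misallocation, so the difference between randomised and actual arm may be negligible.

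Population PK is unaffected, and no primary or key secondary result changes. This is a cheap improvement to descriptive reporting.

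**What to change.** **SAP 2.10.** Summarise by-visit concentrations by actual treatment, limited to the on-treatment period of SAP 2.1.1 (last injection + 30 days), as 2.8.3.4 does for B-cells. SAP 2.1.1 defines that period by randomised arm for efficacy and by actual treatment for compliance, so cite the latter. Flag or tabulate samples by time since last injection, which also shows skipped injections. List off-treatment samples separately.

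Do not restrict the table to samples taken 25–31 days after injection. Under the attendance assumptions above, that would discard 38% to 76% of samples.

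**SAP 2.9.2.** Report treatment-emergent ADA among ofatumumab-treated patients: baseline negative with at least one post-baseline positive, the denominator being patients with evaluable baseline and post-baseline samples. Give baseline positivity its own row.

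**Cost.** SAP wording and a filter on dates already collected. The late PK rows will hold slightly fewer values.

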6.6.3 Immunogenicity

ADA will be assessed to evaluate the immunogenicity potential of ofatumumab. Sampling time points are provided in [Table 6-1](#). Samples for ADA assessment should be taken prior to dosing at the Month 1 visit. For any later ADA visits, if the visit coincides with the day the monthly injection is scheduled, the patient should not take the injection in the morning before coming to the site so that the ADA sample can be drawn before the injection. The ADA sample collection date and time must be entered on the appropriate CRF.

7 Safety monitoring

7.1 Adverse events

An adverse event (AE) is any untoward medical occurrence (e.g., any unfavorable and unintended sign including abnormal laboratory findings, symptom or disease) in a subject or clinical investigation subject after providing written informed consent for participation in the study until the end of study participation. Therefore, an AE may or may not be temporally or causally associated with the use of a medicinal (investigational) product.

In addition, all reports of intentional misuse and abuse of the product are also considered an adverse event irrespective if a clinical event has occurred.

The occurrence of adverse events must be sought by non-directive questioning of the patient at each visit during the study. Adverse events also may be detected when they are volunteered by the patient during or between visits or through physical examination findings, laboratory test findings, or other assessments.

Abnormal laboratory values or test results constitute adverse events only if they fulfill at least one of the following criteria:

- they induce clinical signs or symptoms
- they are considered clinically significant
- they require therapy

Clinically significant abnormal laboratory values or test results must be identified through a review of values outside of normal ranges/clinically notable ranges, significant changes from Baseline or the previous visit, or values which are considered to be non-typical in patient with underlying disease. Investigators have the responsibility for managing the safety of individual patient and identifying adverse events. Clinically notable laboratory findings are defined according to the Common Terminology Criteria for Adverse Events (CTCAE).

Adverse events must be recorded in the Adverse Events CRF under the signs, symptoms or diagnosis associated with them, accompanied by the following information:

- the Common Terminology Criteria AE (CTCAE) grade (1-4)

If CTCAE grading does not exist for an adverse event, use:

1=mild

2=moderate

3=severe

4=life-threatening (see [Section 7.2](#) for definition of SAE)

CTCAE Grade 5 (death) is not used, but is collected as a seriousness criteria and also collected in other CRFs (Study Completion, Death/Survival).

There may be cases where a CTCAE with a grade of 4 (life-threatening) may not necessarily be an SAE (e.g. certain laboratory abnormalities in the absence of meeting other seriousness criteria)

- its relationship to the study treatment
 - Yes
 - No
- its duration (start and end dates) or if the event is ongoing, an outcome of not recovered/not resolved must be reported.
- whether it constitutes a serious adverse event (SAE - See [Section 7.2](#) for definition of SAE) and which seriousness criteria have been met
- action taken regarding (investigational) treatment

All adverse events must be treated appropriately. Treatment may include one or more of the following:

- no action taken (e.g. further observation only)
- study treatment dosage increased/reduced
- study treatment interrupted/withdrawn
- concomitant medication or non-drug therapy given
- patient hospitalized/patient's hospitalization prolonged (see [Section 7.2](#) for definition of SAE)
- its outcome (not recovered/not resolved; recovered/resolved; recovering/resolving, recovered/resolved with sequelae; fatal; or unknown)

Once an adverse event is detected, it must be followed until its resolution or until it is judged to be permanent, and assessment must be made at each visit (or more frequently, if necessary) of any changes in severity, the suspected relationship to the study drug, the interventions if any required to treat it, and the outcome. The action taken to treat the adverse event should be recorded on the Adverse Event CRF.

Information about common side effects already known about the investigational drug (ofatumumab) can be found in the Investigator Brochure (IB). For information about risks and

common side effects related to the comparator (teriflunomide), please refer to the local product label. This information will be included in the patient informed consent and should be discussed with the patient during the study as needed. Any new information regarding the safety profile of ofatumumab that is identified between Investigators Brochure updates will be communicated as appropriate, for example, via an Investigator Notification or an Aggregate Safety Finding. New information might require an update to the informed consent and has then to be discussed with the patient.

The Investigator must also instruct each patient to report any new adverse event (beyond the protocol observation period) that the patient, or the patient's personal physician, believes might reasonably be related to study treatment. This information must be recorded in the Investigator's source documents; however, if the AE meets the criteria of an SAE, it must be reported to Novartis.

